##### **6.3.1.2. Nirogacestat**

PK data analyses will include descriptive summary statistics of predose serum concentrations of nirogacestat by study visit and time point. Box and Whisker plots for predose serum concentrations of nirogacestat by study visit will be generated. PK data from this study maybe pooled with other studies for population PK model development. The correlations between nirogacestat exposure parameters and pharmacodynamic biomarker, efficacy and/or safety outcomes will be explored if data allows. The results of these modeling analyses will be reported separately from the clinical study report.

#### **6.3.2. Immunogenicity**

Immunogenicity data will be analyzed in the Immunogenicity Analysis Set.

The percentage of participants with positive ADA will be summarized. Listings and summary tabulations of the ADA data at baseline and post-baseline will be generated. Samples may also be analyzed for the presence of neutralizing antibodies (NAb), and any data will be similarly summarized. For participants with positive ADA or NAb, the magnitude (titer), time of onset, and duration of ADA or NAb response will also be described, if data permit.

The potential impact of immunogenicity on PK and clinical response including pharmacodynamic markers, safety/tolerability and efficacy will be explored, if warranted by the data. This analysis may be reported separately from the CSR.

## **6.4. Exploratory Endpoints**

### **6.4.1. Biomarker Analysis**

Biomarker data including DNA, RNA, protein, metabolites, or defined cell types resulting from analyses of peripheral blood, and/or BM biospecimens will be assessed based on the Biomarker Set.

Exploratory biomarker endpoints will not be reported in CSR, but in a separate biomarker report.

### **6.4.2. Patient-Reported Outcomes**

The following PRO analyses will be performed to support the CSR development. All other PRO analyses described in the study protocol but are not included in this SAP will be described in detail in a separate PRO analysis plan.

Analysis of the PRO endpoints will be based on the PRO Analysis Set.

### **Completion Status**

The number and percentage of participants who completed these instruments at each time point will be summarized, as will the reasons for non-completion of these measures. An instrument is considered completed if at least one item was answered by the participant.

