## 4. ANALYSIS SETS (POPULATIONS FOR ANALYSIS)

For purposes of analysis, the following analysis sets are defined:

Participant Analysis Set	Description
DLT-Evaluable Analysis Set	
The DLT-evaluable analysis set will include all enrolled participants who receive at least 1 dose of the study intervention in the Phase 1b part of the study and either experience DLT(s) or complete the DLT observation period without DLT. Participants without DLTs who receive less than the minimum requirement of the planned doses of each IP for reason other than treatment-related toxicity are not evaluable for DLTs.
 
The DLT observation period is 35 days from Cycle 0 Day 1 through Cycle 1 Day 28.

090177e196913362\Approved\Approved On: 19-Mar-2021 12:41 (GMT)

	
The minimum required exposure for DLT evaluability is defined as follows:
 
 
• For PF-06863135 (all sub-studies): 4 out of 5 planned doses during the DLT observation period. Participants must be able to receive the full dose on Cycle 1 Day 1 (-1/+3 dosing window) and not require any dose reductions during the DLT observation period;
 
• For nirogacestat (sub-study A): at least 75% of the planned doses and not require any dose reductions during the DLT observation period.
 

Safety Analysis Set	The safety analysis set will include all enrolled participants who received at least 1 dose of study intervention.
PK Analysis Set	
The PK analysis set will include all participants in the safety analysis set who have at least 1 post-dose concentration measurement.
 
The PK parameter analysis set will include all participants in the safety analysis set who have at least one of the PK parameters of interest for PF-06863135.

Immunogenicity Analysis Set	The immunogenicity analysis set will include all participants in the safety analysis set who have at least 1 sample tested for ADA.
Biomarker Analysis Set	
The biomarker analysis set will include all participants in the safety analysis set who have at least 1 baseline biomarker assessment.
 
Analysis sets will be defined separately for biomarkers based on blood, and bone marrow samples.

PRO Analysis Set	The PRO analysis set will include all participants in the safety analysis set who completed a baseline (last PRO assessment prior to or on the first dose of study intervention) and at least 1 post-baseline PRO assessment.

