## 4. ANALYSIS SETS (POPULATIONS FOR ANALYSIS)

See [Section 4 of the master SAP](#) for definitions of analysis sets.

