## **Completion Status**

The number and percentage of participants who completed the PRO at each time point will be summarized, as will the reasons for non-completion. A PRO is considered completed if at least one item was answered by the participant.

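### PRO completion is tabulated in a set already selected for completed forms, so baseline completion is 100% by construction and early losses drop out of the table

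*SAP*

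**What the plan says.** Sub-study A SAP 6.4.2 opens its PRO section with the population: "Analysis of the PRO endpoints will be based on the PRO Analysis Set". Completion Status comes next: "The number and percentage of participants who completed these instruments at each time point will be summarized", together with the reasons for non-completion. It names no population or denominator of its own, and it defines completion: "An instrument is considered completed if at least one item was answered by the participant".

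Sub-study B SAP 6.4.3 has the same structure. It bases the PRO analyses on the PRO Analysis Set, then gives a completion summary with reasons and the rule "A PRO is considered completed if at least one item was answered by the participant". Its only instrument is the QLQ-CIPN20. Sub-study A uses three: QLQ-C30, QLQ-MY20 and QLQ-CIPN20.

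Section 4 of each sub-study SAP sends the reader to the master SAP "for definitions of analysis sets". There, the PRO set is a subset of the Safety Analysis Set, and a member must have "completed a baseline (last PRO assessment prior to or on the first dose of study intervention) and at least 1 post-baseline PRO assessment". Master SAP 6.4.2 orders its own PRO section in the same way.

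Two general provisions also bear on this. Master SAP 5.2.13 bases visit-specific percentages on those remaining in the study at the visit, unless another rule is given. Master SAP 6.6.2.1 reports the size of every analysis set as a percentage of the Safety Analysis Set.

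**The concern.** A completion table exists to show who did not return a form, when, and why. Here its denominator is restricted to people who returned at least two: a baseline form and a later one. A participant who skipped baseline is not in it. Nor is a participant who completed baseline and then progressed, died or stopped before a first post-baseline form.

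This matters because PRO scores are summarized as observed, and master SAP 5.3 rules out imputation unless otherwise specified. In an open-label study, completion by visit with reasons is the main information for judging whether the score summaries come from a selected group. The QLQ-CIPN20 is affected in both sub-studies, and protocol 8.3.8.3 names peripheral neuropathy an important potential risk of elranatamab.

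The one-item rule is a separate weakness. A form can count as completed while contributing nothing to most scales, so the completion count need not match the number of scores behind the summaries.

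**Working it through.** The plan states no completion rate, so there is no figure to reproduce. The first steps compare definitions. The arithmetic after them uses the planned Phase 2 size of about 50 (Sub-study A SAP 2.3) and **assumed** numbers of missing forms.

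**1. Baseline.** Membership of the PRO set requires a completed baseline. With S members, baseline completion is S/S = 100% whatever the true rate, and no reason for baseline non-completion can appear.

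**2. Per instrument.** Section 4 speaks of a baseline and a post-baseline PRO assessment without saying which instrument.
- Sub-study B has one instrument, so 100% is exact.
- In Sub-study A, 100% is exact for each instrument only if the set is built per instrument. If any instrument qualifies a participant, one instrument can fall below 100%. For example, if 3 of 40 members left the QLQ-C30 blank at baseline, it shows 37/40 = 92.5%.

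**3. Does the by-visit rule repair this?** Master SAP 5.2.13 reduces a denominator to those still present. It does not add back people whom the set definition removed.

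**4. Illustration.** Let N = 50, b = participants with no baseline, c = participants with a baseline but no later form, and k = set members completing at a given later visit.
- S = N − b − c
- Baseline: S/S in the set; (N − b)/N of all treated
- Later visit: k/S in the set; between k/N and (k + b)/N of all treated, as none or all of the b participants complete that form

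| Case | b, c, k | S | Baseline: set / all treated | Later visit: set | Later visit: all treated | Excess (points) |
|---|---|---|---|---|---|---|
| a | 2, 2, 36 | 46 | 100% / 96% | 36/46 = 78.3% | 72% to 76% | 2 to 6 |
| b | 5, 5, 30 | 40 | 100% / 90% | 30/40 = 75.0% | 60% to 70% | 5 to 15 |
| c | 10, 10, 20 | 30 | 100% / 80% | 20/30 = 66.7% | 40% to 60% | 7 to 27 |

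**5. The same check with participants still on study.** In case b, suppose the 5 without a later form have left and the other 45 are present. If no baseline-misser completes the form, the rate is 30/45 = 66.7%, against 75.0% in the PRO set. If all 5 do, it is 35/45 = 77.8%, above the PRO-set rate. The usual direction is upward, but it is not guaranteed.

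**6. One-item rule.** One answer is 1/30 = 3.3% of the QLQ-C30 and 1/20 = 5% of the QLQ-MY20. A one-item QLQ-C30 form has no data for 14 of its 15 scales. The SAP does not say whether this meaning of completed also governs entry to the PRO set. If it does, entry is loosened too.

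**The case against.** The strongest reply is that Completion Status names no denominator. Completion is a data-availability summary, arguably not an analysis of a PRO endpoint, so the by-visit rule in master SAP 5.2.13 might apply to everyone still on study. Asking for reasons at each time point would also be odd if baseline could have none. It is true that the denominator is inferred from placement. But in Sub-study A, 6.4.2 announces the PRO analyses that follow, bases PRO analysis on the PRO Analysis Set, and then gives completion first. No text assigns another population. The separate PRO analysis plan mentioned there covers only analyses left out of the SAP, and completion is in it.

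Several stronger claims are tempting, and the documents do not support them:

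- **That this table is the only check, or that losses are wholly hidden.** The disposition summary in master SAP 6.6.2.1 would show the PRO set against the Safety Analysis Set, 40/50 = 80% in case b, and discontinuations by reason. It does not show PRO losses by visit, instrument or reason for a missing form.
- **That every Sub-study A instrument must show 100% at baseline, or that later rates must be inflated.** Steps 2 and 5 show otherwise.
- **That completion should require half the items.** No document gives that threshold, and it would not make completion match the scale counts. Half of a 30-item form can be answered with whole scales blank.
- **That the gap between completion and scorable forms would be invisible.** Master SAP 5.2.13 asks for non-missing and missing counts for continuous variables, and the QLQ-CIPN20 has item-level summaries. The gap can be traced, but not in the completion table.
- **That trial decisions are at risk.** PROs are exploratory and descriptive, and limited to Phase 2 in Sub-study A. The neuropathy enrollment holds use graded adverse events, not the QLQ-CIPN20.

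**Conclusion.** The point holds in a limited form. Read in the natural way, both sub-study SAPs produce a completion table whose baseline rate is fixed at 100% for the PRO assessment as a whole. Participants lost before a first post-baseline form are excluded from the rates and the reasons. Later rates will probably be too high. In the three assumed cases the excess over the all-treated rate runs from about 2 to 27 points, but the true size depends on counts the documents do not give. Against those still on study the direction can reverse if baseline-misses return later forms more often than set members do.

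The conclusion rests on the PRO Analysis Set being the denominator for completion, which follows from placement and not from an explicit statement. If the sponsor intended another denominator, the SAP still needs to say so. The consequence is confined to interpreting exploratory PRO results. The primary ORR analysis, the go/no-go rule and the safety holds are untouched.

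**What to change.** In Sub-study A SAP 6.4.2 and Sub-study B SAP 6.4.3, and for consistency in master SAP 6.4.2:

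1. Calculate completion and reasons for non-completion per instrument in the Safety Analysis Set (Phase 2 participants for Sub-study A).
2. Use participants due the form at that visit as the main denominator and all treated participants as a second. The second is needed because the first drops those who have died or left.
3. Beside each completion count, show the number of forms with enough items answered to score each scale. A fixed cut-off for calling a form complete is then unnecessary.
4. Keep the PRO Analysis Set for score summaries, and state whether it is built per instrument or on any instrument.

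The cost is a few sentences of SAP text and one re-based table from data already collected. The reported completion rates will probably be lower.

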### **EORTC QLQ-C30**

This questionnaire contains 30 questions organized into 5 multi-item functional scales, 3 multi-item symptom scales, a global health/quality of life scale, and 6 single item symptom scales. For each of the 15 scales, the results will be summarized using descriptive statistics including mean, SD, 95% CI, median, minimum, maximum at each timepoint. This will be performed based on the observed values as well as change from baseline values.

### **EORTC QLQ-MY20**

This questionnaire contains 20 questions organized into 2 functional scales and 2 symptom scales. As with QLQ-C30, the analysis of the QLQ-MY20 scales will consist of descriptive statistics based on observed values and change from baseline values.

### **EORTC QLQ-CIPN20**

This questionnaire contains 20 questions which can be grouped into a sensory subscale (9 items), motor subscale (8 items) and autonomic subscale (3 items). The analysis of the QLQ-CIPN20 subscales will consist of descriptive statistics based on observed values and change from baseline values. Number and percent will be summarized for the item-level responses at each visit.

## 6.5. Subset Analyses

All the subset analyses will be exploratory; no adjustment for multiplicity will be performed. Analyses will only be performed if there is sufficient sample size. The determination of whether or not there is sufficient sample size will be defined after enrollment is complete and prior to database lock. As a general rule, analyses of ORR will only be performed if there are  $\geq 10$  participants overall within the defined subset. Deviations from these analyses will be described in the clinical study report.

The following subset analyses will be performed for ORR as determined by investigator for Phase 2 part only based on the Safety Analysis Set:

- Baseline cytogenetics (high vs standard risk);
- EMD at baseline (yes vs no);
- Prior stem cell transplant (yes vs no);
- Disease stage (1-2 vs 3);
- Number of prior therapies ( $\leq 4$ ,  $>4$ );
- Type of myeloma (IgG vs non-IgG vs light chain only);
- Age ( $<65$  vs  $\geq 65$ ;  $<75$  vs  $\geq 75$ ).

ORR in subsets will be presented in a forest plot. Other subset analyses will be performed as well if deemed clinical meaningful and feasible (sufficient sample size).

## 6.6. Baseline and Other Summaries and Analyses

### 6.6.1. Baseline Summaries

See [Section 6.5.1 of the master SAP](#) for baseline summaries.

### 6.6.2. Study Conduct and Participant Disposition

See [Section 6.5.2 of the master SAP](#) for summaries of study conduct and participant disposition.

### 6.6.3. Study Intervention Exposure

Exposure will be summarized based on the Safety Analysis Set (SAS). will be calculated based on the total number of participants in SAS.

#### 6.6.3.1. Exposure to Elranatamab

The summary of treatment exposure to elranatamab will include the following information:

- Treatment duration (weeks);
- Number of cycles started per participant (mean, median, min, max);

- Number and percent of participants starting a cycle (any cycle, cycle 0, 1, 2, 3, 4, 5, 6, 7, 8, 9, 10, 11, >=12 cycles);
- Total cumulative dose (mg);
- Overall dose intensity (mg/week);
- Overall relative dose (%);
- Overall relative dose intensity (%);
- Number and percent of participants after 6 cycles who switched from QW to Q2W;

CCI

The treatment duration of elranatamab (in weeks) during the study for a participant is defined as:

$$\text{Treatment duration (weeks)} = (\text{last dose date} - \text{first dose date} + 1)/7$$

Planned treatment duration and intended treatment duration are needed to calculate dose intensity (DI) and relative dose intensity (RDI). It is defined as follows:

- Planned treatment duration (weeks) = 1 (1 week for Cycle 0) + number of cycles started  $\times$  4 - (number of weeks in the last cycle after permanent treatment discontinuation or data cutoff for those on-treatment).

Intended treatment duration (weeks) = (last zero/non-zero dose date – first dose date)/7 + ( 1 if on QW or 2 if on Q2W CCI ). If C0D4 is the last visit, duration is 1 week if C0D4 occurred by then; The planned dose for a given cycle is defined as:

- Cycle 0:
  - Planned dose (mg/cycle) = Planned priming dose(s) per protocol during C0
- After Cycle 0:
  - If the participant is on QW dosing schedule for the cycle:  
Planned dose (mg/cycle) = Full dose  $\times$  4
  - If the participant is on Q2W dosing schedule for the cycle:  
Planned dose (mg/cycle) = Full dose  $\times$  2

CCI

**Note:** Full dose= 4 ,12, 32, or 76mg depending on DLs. For the last cycle, subtract planned doses after a participant permanently discontinues treatment or data cutoff for those on-treatment.

Total planned dose is the sum of the total planned dose across all cycles.

The total cumulative dose (mg) of elranatamab is the sum of the actual doses that the participant received during the study; the cumulative dose (mg) of elranatamab per cycle is the sum of the actual doses that the participant received within that cycle (ie, total dose administered [mg]).

The DI, relative dose (RD), and the RDI will be calculated for each participant across all cycles and also for each individual cycle:

- Overall DI (mg/week) = Total cumulative dose (mg)/Intended treatment duration (weeks)
- Overall planned DI (mg/week) = Total planned dose (mg)/ Planned treatment duration (weeks)

The RD and RDI are defined as follows:

- Overall RD (%) = [Total cumulative dose (mg) /Total planned dose (mg)] × 100;
- Overall RDI (%) = [Overall DI (mg/week) /Overall Planned DI (mg/week)] × 100.

Cycle DI and Cycle RDI will be summarized and plotted vs time (weeks).

#### **6.6.3.2. Exposure to Nirogacestat**

Nirogacestat is administered in 28-day cycles starting on C1D1. Dose may eventually be reduced or even discontinued if the participant responds well to treatment. The summary of treatment exposure to nirogacestat will include the following information:

- Treatment duration (weeks);
- Total cumulative dose (mg);
- Total planned cumulative dose (mg);
- Overall dose intensity (mg/week);
- Overall relative dose intensity (%).

The duration of nirogacestat (in weeks) during the study for a participant is defined as:

$$\text{Treatment duration (weeks)} = (\text{last dose date} - \text{first dose date} + 1)/7$$

Planned treatment duration, intended treatment duration, planned dose and planned DI is needed to calculate DI and RDI. The planned treatment duration is defined as:

- Planned treatment duration (weeks) = (number of cycles started x 4) - (number of weeks in the last cycle after permanent nirogacestat discontinuation or data cutoff for those on-treatment).
- Intended treatment duration (weeks) = (last zero/non-zero dose date – first dose date+1)/7 ;
- Planned dose per cycle (mg/cycle) = total planned daily dose per cycle×28;

**Note:** For last cycle, subtract planned doses after a participant permanently discontinues treatment or data cutoff for those on-treatment.

The total planned dose is the sum of the total planned dose across all cycles.

The total cumulative dose (mg) of nirogacestat is the sum of the dosage that the participant received during the study (ie, total dose administered [mg]).

The overall planned DI is defined as:

- Overall Planned DI (mg/week) = Total planned dose (mg)/(planned treatment duration in weeks).

The overall DI and RDI of nirogacestat will be calculated for each participant during the study.

- Overall DI (mg/week) = Total cumulative dose (mg) / Intended treatment duration (weeks);
- Overall RD (%) = [Total cumulative dose (mg) / Total planned dose (mg)] × 100;
- Overall RDI (%) = [Overall DI (mg/week) / Overall Planned DI (mg/week)] × 100.

### 6.6.3.3. Dose Reductions, Interruptions, and Delays

#### Dose Reduction

Dose reduction of elranatamab is not permitted.

For nirogacestat, a dose reduction is defined as a non-zero dose that is less than the planned dose in the protocol. For nirogacestat, the number and percentage of participants with at least 1 dose reduction as well as a breakdown of dose reductions (1/2/3/≥4) will be summarized by dose cohort ( Phase 1b dose escalation part) and Phase 2 part. In addition, the number and percentage of participants with at least 1 dose reduction due to AE will also be summarized. Planned decreases in nirogacestat for participants on dose levels 3A/3B or 4A/4B due to

objective response of confirmed VGPR via 2 consecutive assessments or CR (or better) via bone marrow assessment are not counted as reductions in this analysis.

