### 6.6.3.1. Dose Reductions, Interruptions, and Delays

#### **Dose Reduction**

For PF-06863135 and nirogacestat, a dose reduction is defined as a non-zero dose that is less than the prior dose and less than the planned dose in the protocol.

The number and percentage of participants with at least 1 dose reduction as well as a breakdown of dose reductions (1/2/3/ $\geq$ 4) will be summarized.

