**Table 2. Study Intervention Dose Levels and Administration**

Dose Levels (DL)	Elranatamab	Nirogacestat
1 (starting dose level)	Priming Dose: 4 mg C0D1 SC Full Dose: 4 mg C1D1 SC, weekly thereafter b	100 mg PO BID continuous starting on C1D1 until response a
2	2 Step-up Priming Dose: 4 mg C0D1 SC / 8 mg C0D4 SC Full Dose: 12 mg C1D1 SC, weekly thereafter b	100 mg PO BID continuous starting on C1D1 until response a
3	2 Step-up Priming Dose: 12 mg C0D1 SC / 32 mg C0D4 SC Full Dose: 32 mg C1D1 SC, weekly thereafter b	100 mg PO BID continuous starting on C1D1 until response a
Nirogacestat De-Escalation Levels		
3A	2 Step-up Priming Dose: 12 mg C0D1 SC / 32 mg C0D4 SC Full Dose: 32 mg C1D1 SC, weekly thereafter b	100 mg PO QD continuous starting on C1D1 until response a
4A	2 Step-up Priming Dose: 12 mg C0D1 SC / 32 mg C0D4 SC Full Dose: 76 mg C1D1 SC, weekly thereafter b,c	100 mg PO QD continuous starting on C1D1 until response a
3B	2 Step-up Priming Dose: 12 mg C0D1 SC / 32 mg C0D4 SC Full Dose: 32 mg C1D1 SC, weekly thereafter b	50 mg PO QD continuous starting on C1D1 until response a
4B	2 Step-up Priming Dose: 12 mg C0D1 SC / 32 mg C0D4 SC Full Dose: 76 mg C1D1 SC, weekly thereafter b,c	50 mg PO QD continuous starting on C1D1 until response a

- a. For Dose levels 3A/3B and 4A/4B, nirogacestat will be adjusted to 50 mg QD continuous at time of confirmed VGPR. Once CR (or better) is confirmed, nirogacestat will be permanently discontinued. For all other dose levels, nirogacestat can be continued or adjusted based on this guidance, per investigator discretion. See Section 6.1.1.5.
- b. Starting at Cycle 7, if a participant has received QW dosing for at least 6 cycles and PR or better persisting for ≥2 months, dose interval will be changed from QW to Q2W. See Schedule of Activities.
- c. For participants on Dose levels 4A and 4B receiving CCI dosing, CCI the dose interval will be changed to CCI

090177e1a0f4f44c\Approved\Approved On: 14-Jun-2024 22:12 (GMT)

CCI

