#### 6.6.3.4. Dose Reductions, Interruptions, and Delays

##### **Dose Reduction**

A dose reduction is defined as a nonzero dose that is less than the planned dose. The planned dose is the same as the prior dose except for elranatamab at C0D4 and C0D8.

For each study treatment, the number and percentage of participants with at least 1 dose reduction as well as a breakdown of dose reductions (1/2/3/ ≥4) will be summarized by dose cohort (dose escalation part) and treatment arm (dose expansion). In addition, the number and percentage of participants with at least 1 dose reduction due to an AE will also be summarized.

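### Sub-study A's nirogacestat dose-reduction rule can count one sustained reduction several times, and its exclusion of response-driven decreases leaves out dose levels 1–3

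*SAP*

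**What the plan says.** Three SAPs define a dose reduction, in three ways.

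- **Sub-study A SAP 6.6.3.3:** for nirogacestat, "a dose reduction is defined as a non-zero dose that is less than the planned dose in the protocol". The table reports participants with at least one reduction and a breakdown by number (1, 2, 3, ≥4), by Phase 1b dose cohort and for Phase 2. It adds that "the number and percentage of participants with at least 1 dose reduction due to AE will also be summarized".
- **Master SAP 6.6.3.1:** "a non-zero dose that is less than the prior dose and less than the planned dose", so both conditions must hold.
- **Sub-study B SAP 6.6.3.4:** a reduction is a non-zero dose below plan, but "The planned dose is the same as the prior dose except for elranatamab at C0D4 and C0D8". Tying plan to prior dose has the same effect.

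For interruptions of nirogacestat, Sub-study A SAP 6.6.3.3 does give a counting rule: consecutive zero-dose days with the same reason count once, with three worked examples. It gives no such rule for reductions.

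On response-driven decreases, Sub-study A SAP Table 2 footnote a requires nirogacestat to go to 50 mg QD at confirmed VGPR, and to stop at confirmed CR or better, at levels 3A/3B and 4A/4B. It then adds: "For all other dose levels, nirogacestat can be continued or adjusted based on this guidance, per investigator discretion". The exclusion in 6.6.3.3 is narrower. It covers "Planned decreases in nirogacestat for participants on dose levels 3A/3B or 4A/4B due to" confirmed VGPR or CR, and names no other level.

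**The concern.** A 1/2/3/≥4 breakdown is meant to show how often the dose had to be lowered. If every dose below plan qualifies, it can instead show how long participants stayed on a lowered dose. The master SAP and Sub-study B both guard against this. The Sub-study A change log (Table 1) mentions only the elranatamab clarification for this section and gives no reason for dropping the prior-dose condition.

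The second problem is one of labelling across columns. Reductions are tabulated by dose cohort. The same step to 50 mg QD after a VGPR is counted as a reduction at levels 1–3 and excluded at 3A and 4A. Cohorts are small (Sub-study A SAP 5.1.1.1 plans a minimum of 2 to 6 DLT-evaluable participants per level), so one or two such participants would visibly move a percentage.

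**Working it through.** No sample size, power or error rate is involved. The check applies each rule to simple dosing histories.

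**Check against the plan's own figures.** Applying the interruption rule to the three worked examples in 6.6.3.3 returns 1, 2 and 2, as stated. The planned nirogacestat dose for the DLT period, 100 × 2 × 28 = 5,600 mg, matches Sub-study A SAP 6.1.1.

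**Step 1: recounting.** Assume a planned dose of 200 mg/day (100 mg BID) and one step-down to 100 mg/day that is then held. The 100 mg/day value is illustrative only.

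- Sub-study A rule: count records with 0 < dose < planned.
- Master rule: the same, and dose < prior dose.

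| How dosing is recorded | Length of reduction | Sub-study A count | Master count |
|---|---|---|---|
| Per day | 1, 2, 3, 4, 28, 56 days | 1, 2, 3, 4, 28, 56 | 1 each time |
| Per cycle | 1, 2, 3, 4 cycles | 1, 2, 3, 4 | 1 each time |
| One record per constant-dose interval | any, uninterrupted | 1 | 1 |

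With daily records the participant reaches the ≥4 category on the fourth reduced day. With per-cycle records this happens in the fourth reduced cycle. In every row both rules agree that the participant had at least one reduction, so that percentage, overall and due to AE, is the same.

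**Step 2: response-driven decreases.** Set footnote a beside the exclusion, holding the planned dose at its assigned value:

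| Level | Planned mg/day | Change to 50 mg QD at VGPR | Counted as a reduction? |
|---|---|---|---|
| 1–3 | 200 | allowed, discretionary | yes |
| 3A, 4A | 100 | required | no, excluded |
| 3B, 4B | 50 | no decrease (already 50) | no |

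Stopping at CR or better is a zero dose, so it is not a reduction at any level. The mismatch is therefore levels 1–3 against 3A/4A, at VGPR.

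For scale, assume a participant with no other reduction. One discretionary decrease then moves the percentage at that level by 1/6 = 16.7 points in a cohort of 6, or 1/2 = 50 points in a cohort of 2. With 0 to 6 such decreases in a cohort of 6, the range is 0% to 100%. The documents do not say how many to expect.

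**Step 3: relative dose.** Sub-study A SAP 6.6.3.2 bases planned dose per cycle on the planned daily dose × 28. It does not say whether that daily dose changes after a response-driven decrease. Take a level 3 participant lowered from 200 to 50 mg/day after 3 of 12 cycles:

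- Dose received: 3 × 28 × 200 + 9 × 28 × 50 = 16,800 + 12,600 = 29,400 mg.
- If the planned dose stays at 200 mg/day: 12 × 28 × 200 = 67,200 mg, and relative dose = 29,400 / 67,200 = 43.8%.
- If the planned dose follows the adjustment: 29,400 / 29,400 = 100%.

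Both readings fit the text.

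**The case against.** A reader might infer that the tolerability comparison between the BID and QD levels is wrong. The documents do not support that. No such comparison is planned; reductions are tabulated descriptively by cohort. Sub-study A SAP 5.1.2.1 bases the RP2D on the estimated DLT probability together with later safety, activity, PK and pharmacodynamic data, and names neither reduction counts nor relative dose intensity. Reductions due to AE are summarized separately in the same section. Master SAP 6.7.1, reached through Sub-study A SAP 6.7, tabulates TEAEs leading to reduction of the partner drug as the investigator reports them. A response-driven decrease enters neither, so responders are not turned into poor tolerators in the tables that address toxicity.

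It is also true that recounting depends on how dosing is recorded, which the documents do not state. With one record per constant-dose interval, an uninterrupted reduction counts once.

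The narrower exclusion could be deliberate, because the decrease is required at 3A–4B and discretionary at levels 1–3. One could also argue that an adjusted dose becomes the new planned dose, in which case it is not below plan; footnote a points to a Section 6.1.1.5 that is not among the supplied documents. That argument has a cost. If the planned dose updated by itself, the exclusion at 3A–4B would be unnecessary, and its presence suggests that such decreases would otherwise count. Even a deliberate distinction leaves one column heading with two meanings.

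**Conclusion.** The definition is wrong as written, and the consequence is minor. Followed literally, it can place a single sustained step-down in the ≥4 category under daily or per-cycle recording, where the master SAP's rule gives 1. The participants-with-at-least-one-reduction figures are not affected by this. The exclusion makes the all-cause percentage with at least one reduction not like for like between levels 1–3 and 3A/4A. This assumes that the planned dose stays as assigned and that investigators use the discretion footnote a gives them. The size is unknown and may be zero.

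The 43.8% relative dose is only an illustration, conditional on the planned dose staying at 200 mg/day. No primary or secondary endpoint, decision rule or AE-specific summary is touched.

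**What to change.** Make three edits to the Sub-study A SAP:

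1. In 6.6.3.3, define a nirogacestat reduction as a non-zero dose below both the prior dose and the planned dose, as in master SAP 6.6.3.1, so that a sustained reduction counts once. State that the prior dose is the last non-zero dose. Otherwise a sequence such as 200, 0, 100 mg/day would be missed, because 100 is not below 0.
2. Apply the exclusion of response-driven decreases at every dose level, and in Phase 2, where footnote a permits the adjustment. Identify them by the recorded reason for dose change.
3. In 6.6.3.2, state whether the planned daily dose used for relative dose and relative dose intensity follows such an adjustment, and apply the choice at all levels.

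The cost is a few sentences and some programming. The one dependency is that the reason for dose change must be recorded well enough at levels 1–3 to separate response from toxicity. No dosing rule changes.
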